AIC316-03-I-01

Summary of the Clinical Trial Protocol and Statistical Plan

**A single-center, open-label, 2-period, fixed-sequence Phase 1 trial
to evaluate the effect of esomeprazole on the pharmacokinetics of pritelivir**

NCT number: NCT05513625

Investigational drug: Pritelivir

Sponsor: AiCuris Anti-infective Cures AG

Address: [name]
[name]
Germany

Finalization dates:

Summary of the Clinical Trial
Protocol and Statistical Plan, V1.0: 16Sep2022

Clinical Trial Protocol,
V1.0: 04Jun2020

Safety Statistical Analysis Plan,
V2.0: 21Jul2020

Pharmacokinetic Statistical
Analysis Plan, V1.0: 01Jul2020

SUMMARY OF THE CLINICAL TRIAL PROTOCOL AND STATISTICAL PLAN

Name of Sponsor/Company:	AiCuris Anti-infective Cures GmbH					
Title of the trial: A single-center, open-label, 2-period, fixed-sequence Phase 1 trial to evaluate the effect of esomeprazole on the pharmacokinetics of pritelivir						
Principal Investigator: [name]						
Trial center(s): Medpace Clinical Pharmacology [name]						
Planned trial period: First Subject First Visit: Jul 2020 Last Subject Last Visit Sep 2020	Phase of development: Phase 1					
Objectives: 
• To investigate the effect of esomeprazole on the pharmacokinetics of pritelivir• To investigate the pharmacokinetics of pritelivir metabolites AIC090015, AIC090105 and AIC090015-acetylglucuronides• To investigate the safety and tolerability of pritelivir						
Trial design: This will be a single-center, open-label, 2-period, fixed-sequence Phase 1 trial in 18 healthy adult male and female subjects (at least 7 subjects per sex). All subjects will receive treatment 1 (T1; single dose of 100 mg pritelivir will be administered on Day 1) in the first period, followed by treatment 2 (T2; single dose of 100 mg pritelivir will be administered on Day 1 and 40 mg esomeprazole will be administered qd from Day -3 to Day 1) in the second period. The wash-out period between pritelivir administrations in T1 and T2 is at least 4 weeks.						
Number of subjects (planned): 18						
Diagnosis and main criteria for inclusion: Healthy adult male and female subjects (at least 7 subjects per sex) of any ethnic origin, aged 18 to 45 years inclusive.						
Test product, dose and mode of administration: Oral 100 mg pritelivir tablets Oral 40 mg esomeprazole tablets (Nexium®)						
Duration of treatment: In Treatment Period 1: Pritelivir: single dose of 100 mg on Day 1						

In Treatment Period 2:

4 days

Esomeprazole: 40 mg qd from Day -3 to Day 1, inclusive

Pritelivir: single dose of 100 mg on Day 1

Reference therapy, dose and mode of administration, batch number(s):

Not applicable.

Criteria for evaluation:

Efficacy

Not applicable.

Pharmacokinetics**Primary variables:**

- $AUC_{0-\infty}$, $AUC_{0-\text{last}}$, C_{\max} of pritelivir in plasma

Secondary variables:

- t_{\max} , t_{lag} , $t_{1/2z}$, CL/F , V_d/F , MRT of pritelivir in plasma
- $AUC_{0-\infty}$, $AUC_{0-\text{last}}$, C_{\max} , t_{\max} , t_{lag} , $t_{1/2z}$, MRT of metabolites AIC090015, AIC090105 and AIC090015-acyl glucuronides in plasma
- The ratio between each of the metabolites AIC090015, AIC090105 and AIC090015-acyl glucuronides versus pritelivir will be calculated for $AUC_{0-\infty}$, $AUC_{0-\text{last}}$

Pharmacokinetic profile will be determined in each period on Day 1 for 360 hours.

Pharmacogenomics/gene expression:

- Post-hoc analysis of alleles associated with altered drug metabolism/ disposition may be determined.

Safety

- Overall tolerability
- Nature, frequency, duration, severity and causality of adverse events
- Clinical laboratory parameters
- Vital signs (blood pressure, pulse rate)
- Standard 12-lead ECG

Statistical methods:**Pharmacokinetic data**

The Pharmacokinetic Set (PKS) will include all subjects in the Safety Set (SS) with at least 1 plasma concentration time point for inclusion in the PK analysis. The PKS will be used for the PK analyses.

Descriptive statistics will be calculated for plasma concentrations of pritelivir and derived PK parameters. Statistics include sample size (n), mean, standard deviation (SD), %CV, geometric mean, median, minimum and maximum.

The relative bioavailability of pritelivir with respect to the primary variables $AUC_{0-\infty}$, $AUC_{0-\text{last}}$ and C_{\max} will be explored based on the log transformed data with an analysis of variance model with treatment (as fixed effect) and subject (as random effect). Point estimates (GMR) and 90% confidence intervals (90% CIs) will be computed for the ratio T_2 (test) / T_1 (reference) to evaluate the effect of esomeprazole on pritelivir PK under fasted conditions.

Safety data

Safety data analysis will be conducted on the Safety Set. Statistical analysis of the safety data will be limited to descriptive summaries.

The results of AE recording, vital signs, 12-lead ECGs, clinical laboratory investigations, and physical examinations will be listed by subject and analyzed by descriptive statistics as appropriate.

All adverse events will be coded according to the Medical Dictionary for Regulatory Activities (MedDRA). Incidences of treatment-emergent adverse events (TEAE) that began after the start of trial treatment (post-dose on Day 1 to End of trial examination) will be summarized at 3 levels: the overall subject level (occurrence of at least one TEAE), primary System Organ Class level, and preferred term level. All adverse events will be listed together with information on onset, duration, frequency, intensity, seriousness, relationship to IMP, outcome, and action taken.

Laboratory data will be presented in summary statistics of raw data and change from baseline values (mean, median, standard deviation, minimum, maximum), and by flagging values outside the reference range in data listings. Vital signs will be summarized presenting statistics of raw data and change from baseline values (mean, median, standard deviation, minimum and maximum).

ECG data will be summarized presenting statistics of raw data and change from baseline values (mean, median, standard deviation, minimum and maximum). In addition, 12-lead ECGs will be analyzed with a focus on the incidence and extent of QTc prolongation. QTc will be calculated according to Fridericia formula. Frequencies for classes of absolute values and differences from baseline will be provided according to the classifications defined by ICH-E14.

The World Health Organization Drug Dictionary (WHO-DD) will be used for coding of concomitant medications (except IMPs).

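### The TEAE incidence counts events by onset only, so an adverse event present before the first dose that worsens afterwards is left out and the incidence may be understated

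*Combined protocol and SAP*

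**What the plan says.** All of the text below is in the Summary of the Clinical Trial Protocol and Statistical Plan.

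- **Statistical methods, Safety data (counting rule).** The sentence that sets the population of events opens "Incidences of treatment-emergent adverse events (TEAE) that began after the start of trial treatment (post-dose on Day 1 to End of trial examination) will be" and continues with the levels: these "will be summarized at 3 levels: the overall subject level (occurrence of at least one TEAE), primary System Organ Class level, and preferred term level".
- **Statistical methods, Safety data (listing).** "All adverse events will be listed together with information on onset, duration, frequency, intensity, seriousness, relationship to IMP, outcome, and action taken". The listing covers every adverse event, treatment-emergent or not.
- **Criteria for evaluation, Safety.** The adverse event criterion is "Nature, frequency, duration, severity and causality of adverse events".
- **Trial design.** All subjects take pritelivir alone (T1) and then pritelivir with esomeprazole (T2). On the gap between them: "The wash-out period between pritelivir administrations in T1 and T2 is at least 4 weeks".
- **Sample size.** "Number of subjects (planned): 18".

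Nowhere does the text say that a worsening after dosing makes an event treatment-emergent, or that a worsened event is recorded again with a new onset date. It does not describe an incidence by treatment, by period or by intensity.

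**The concern.** A treatment can show its harm by starting an event or by aggravating one that is already there. The counting rule recognises only the first. Suppose a subject has a mild headache before the Period 1 dose that becomes severe and is judged drug-related after it. The headache began before treatment, so it enters no incidence.

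Safety and tolerability of pritelivir is one of the three objectives. Its analysis is descriptive, and the TEAE incidence is the only adverse event summary that the plan specifies in detail. Severity is a named criterion and intensity is listed for each event, but neither affects the count. Laboratory values, vital signs and ECG are all summarised as change from baseline, so a deterioration from a pre-dose state is captured there. Adverse events have no counterpart to this.

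**Working it through.** The plan states no figure to reproduce: it gives no adverse event rate and no safety sample-size argument. The check is therefore a reading of the rule, followed by its scale.

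**Step 1: which events the rule leaves out.** Day 1 exists in both periods, and the text does not tie the counting window to one of them. Both readings are set out here.

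| Event | One window from the first dose to the end of the trial | Window restarting in each period |
|---|---|---|
| Present before the Period 1 dose, worsens after it | Not counted at any level | Not counted at any level |
| Began after the Period 1 dose, still present at the Period 2 dose, worsens after that | Already counted at all three levels; the worsening would add no subject | Onset lies before the Period 2 dose, so it adds nothing to a T2 incidence, if one is produced |

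The first row holds under either reading. The second row is an omission only if TEAEs are also tabulated by period or treatment, which the text does not state.

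**Step 2: direction.** Let O be the subjects with an event that began after dosing, and W those with a pre-existing event that worsened after dosing. The plan counts |O|. A rule that uses onset or worsening counts |O ∪ W|. Since |O| ≤ |O ∪ W|, the plan's incidence can equal the broader one or fall below it, but cannot exceed it. The shortfall is the number of subjects in W who are not in O. A subject who also has another TEAE is already counted at the overall level, so for that subject only the System Organ Class or preferred-term row can change.

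**Step 3: size per affected subject.** With n = 18 planned, each subject in W and not in O moves the relevant incidence by 1/18 = 5.6 percentage points. For example, 4/18 = 22.2% would become 5/18 = 27.8%. For a preferred term with one such case and no other, the table shows 0/18 (exact 95% CI 0 to 18.5%) instead of 1/18 = 5.6% (0.1 to 27.3%).

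**Step 4: how often.** The documents do not say. For scale only, assume that a share q of subjects has such an event. The expected number is 18q, and the chance of at least one is 1 − (1 − q)^18.

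| q (assumed) | Expected number in 18 | Chance of at least one |
|---|---|---|
| 1% | 0.18 | 16.5% |
| 2% | 0.36 | 30.5% |
| 5% | 0.90 | 60.3% |
| 10% | 1.80 | 85.0% |

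Nothing in the documents supports any particular row, and q could be close to zero.

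**The case against.** The strongest case against the point has four parts.

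- **The second dose.** A reader might infer that the rule understates T2 in particular, because events carried over from Period 1 can exist only at the second dose. The documents do not support this. No T2 incidence is described, and with a single trial-level window an event that began after the first dose is already counted. A carried-over event must also last through a wash-out of at least 4 weeks and then worsen. Omissions can occur at the first dose too, and there are no rates with which to compare the two. This part of the objection stands.
- **Visibility.** Worsened events are not lost. Every adverse event is listed with onset, intensity, seriousness and relationship, and with 18 subjects the listing can be read in full. The plan also allows further descriptive analysis of adverse events where appropriate. This limits the harm, but that general allowance specifies no table, and the incidence stays incomplete.
- **Recording convention.** If the site enters a worsening as a new event, it has a post-dose onset and the existing rule counts it. That is correct, and it is why the incidence *may* be understated rather than *is*. The text does not say which convention applies.
- **Source.** The public text is a summary and names a separate Safety Statistical Analysis Plan, V2.0, which is not shown and might define TEAEs more fully. If it does, the summary sentence still needs to be brought into line.

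The subjects are healthy adults aged 18 to 45 who take two single doses of pritelivir, so few pre-existing events are likely.

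**Conclusion.** The point holds in a limited form. As written, the rule excludes from all three incidence levels any event that was present before the first dose and worsened after it. The effect is one-directional, at most 5.6 percentage points per affected subject with 18 subjects, and of unknown frequency. It assumes that worsenings are not entered as new events and that the unseen safety plan has no worsening clause.

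Two stronger conclusions should not be drawn. A bias against T2 would need a by-treatment or by-period table that the plan does not state. The probabilities in the table above follow from assumed rates and are not evidence that a case is likely. The pharmacokinetic comparison and its 90% confidence intervals are unaffected. This is a definition worth correcting because the correction is cheap and safety is a stated objective; it does not threaten the trial's main result.

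**What to change.** - **Definition.** Define TEAEs as adverse events that began, or increased in intensity, after the first dose of trial treatment. Anchoring to the first dose, rather than to pritelivir dosing on Day 1 of a period, keeps events that begin on the esomeprazole-only days of Period 2 within the count.
- **Recording.** Have the site record the date and grade of each increase in intensity, or enter the increase as a new event, and state which convention is used.
- **By-treatment tables.** If TEAEs are tabulated by treatment or period, count a worsening in the treatment during which it occurred, at the increased intensity.
- **Listing.** Leave the listing of all adverse events as it is.

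The cost is one or two sentences in the safety analysis plan and one CRF completion instruction, with no extra visits, procedures or subjects. The downside is that reported incidence may be slightly higher and a worsened event can appear under both treatments, which a table footnote can explain. If the full safety plan already has such a rule, only the summary sentence needs to be aligned.
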